5.8 Randomization/Drug Assignment

All subjects will be assigned a unique identification number by the IRT at the screening visit. For subjects who rescreen, the screening number assigned by the IRT at the initial screening visit should be used. The IRT will assign a randomization number that will encode the subject's treatment group assignment according to the randomization schedule at Visit 2.

Eligible subjects will be randomized to BOTOX 155 U, BOTOX 195 U, or placebo in a 1:1:1 ratio. Randomization in this study will be performed at the country level, and randomization stratification factors will include [REDACTED] (yes/no), and \geq [REDACTED] monthly migraine days at baseline (yes/no). [REDACTED] is based on medical history and patient interview. The monthly migraine days count at baseline is generated in the full eligibility report using e-Diary data of the 28 days prior to Visit 2; no manual calculation is required.

All AbbVie personnel with direct oversight of the conduct and management of the trial (with the exception of AbbVie Drug Supply Management Team), the investigator, study site personnel, and the subject will remain blinded to each subject's treatment throughout the study. To maintain the blind, the BOTOX and placebo vials provided for the study will be identical in appearance. In addition, an IDR will add preservative-free saline to each vial and draw the study drug into syringes to be injected. To further facilitate blinding, all subjects will receive 39 injections in the prespecified injection sites at all treatment cycles during the double-blind phase (BOTOX 155 U: 31 sites with active study drug and 8 sites with placebo; BOTOX 195 U: 39 sites with active study drug; placebo: 39 sites with placebo).

When necessary for the safety and proper treatment of the subject, the investigator can unmask the subject's treatment assignment to determine which treatment was assigned and institute appropriate follow-up care. The IRT will provide unrestricted and immediate access to unblinded subject treatment information. The responsibility to break the treatment code in emergency situations resides solely with the investigator. The investigator should inform the AbbVie medical contact of the unmasking. The reason for breaking the code must be recorded in the subject's eCRF.

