The analysis results of the change from baseline in monthly headache days, MSQ v2.1 RFR domain score, monthly acute headache medication days, and AIM-D Physical Impairment domain score (or HIT-6 score [for Europe]) across Months 5 and 6 will come from the same type of MMRM analysis of observed data used for the primary efficacy endpoint, except that the baseline covariates will be monthly headache days, MSQ v2.1 RFR domain score, monthly acute headache medication days, and AIM-D Physical Impairment domain score (or HIT-6 score [for Europe]), respectively.

Logistic regression will be used to analyze responder variables using the same ANCOVA analysis model described for the primary variable (i.e., the MMRM model used for the primary analysis, but without repeat measures). The proportion of subjects with 50% reduction in the change from baseline in monthly migraine days across Months 5 and 6 will be summarized, along with p-values from the logistic regression. The primary assessment will be the pairwise comparison of each BOTOX dose versus placebo. A sensitivity analysis will use the same logistic model after imputation of missing data for the underlying primary variable by the mLOCF rate-change method, as described above. Alternatively, GLIMMIX models for repeated measures of binary data might be used in place of MMRM models; if so, the methodology will be described in the SAP.

Summary and Analysis of Other Endpoints

The other endpoints are defined in Section 3.4. These endpoints are not planned to be included in the multiplicity control. Hence, results will be considered descriptive and potentially supportive of the results for the primary and secondary endpoints.

The comparisons of interest for each of the other endpoints will be the pairwise comparisons of each BOTOX dose (195 U and 155 U) versus placebo, with no statistical comparison between the BOTOX doses. Specific details of the statistical analysis of other efficacy endpoints will be described in the SAP.

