2.4 Sample Size Determination

For the primary endpoint of change from baseline in the frequency of monthly migraine days to the primary time point (8 weeks ending with Week 24), power and sample size calculations assume a 2-sided false-positive error level of alpha = 0.05, with multiple comparisons accommodated by gatekeeping.

Under a 1:1:1 randomization ratio, 259 subjects in each of the BOTOX dose groups and the placebo group at the primary time point will provide 90% power to detect a mean difference of [REDACTED] days between the groups for tests at alpha 0.05 and to detect a mean difference of [REDACTED] days for any tests done at alpha 0.025. These power calculations used a standard deviation estimate of [REDACTED], based on data for the month ending with Day 180 in EM Phase 2 studies for the subgroup of subjects with 8 to 14 migraine/probable migraine days at baseline (AbbVie data on file, Study 191622-037/509). Thus, the sample size is based on an effect size of [REDACTED].

With approximately 125 investigational sites planned, it is recommended that no site randomize more than approximately 12 subjects (i.e., twice the proportional share of 1 more site $2 \times [777/126]$). Due to enrollment challenges a maximum number of 24 subjects (around 3% of 777 subjects) randomized per site was allowed.

Calculations were done by using the commercial software nQuery Advisor® version 7.0, using a 2-sample Student's t-test with equal variances.

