A mixed model for repeated measures (MMRM) analysis will be used for the primary analysis, using data for baseline and each month of the double-blind, placebo-controlled phase (i.e., months ending with Weeks 4, 8, 12, 16, 20, and 24). The statistical model will include treatment (BOTOX 195 U, BOTOX 155 U, and placebo), month, country, strata of [REDACTED], and treatment group-by-month interaction as fixed effects, with the baseline number of monthly migraine days as a covariate, included as a continuous variable rather than as the binomial stratification variable. Subject and residual errors will be random effects. Model parameters will be estimated using a restricted maximum likelihood method incorporating all observed data during the double-blind phase. Unstructured covariance structure will be used. Toeplitz or compound symmetry may be considered if convergency issues arise for the unstructured covariance structure. The Kenward-Roger approximation will be used to estimate denominator degrees of freedom. Contrasts will be constructed to obtain the average treatment effects across Months 5 and 6 to compare each BOTOX dose (195 U and 155 U) to placebo group. The ITT population will be used for primary and sensitivity analyses. A few subjects (less than 1%) who did not have post-baseline scores will not be included in the primary MMRM due to having missing values for the dependent variable. These subjects will be included in sensitivity analyses and have post-baseline scores imputed as described in Section 9.2. The primary comparisons of interest will be the pairwise comparisons of each BOTOX dose (195 U and 155 U) versus placebo across Months 5 and 6.

Each dose comparison will be analyzed across primary and secondary endpoints in the order described in Section 13.0, using a ranked-order serial gatekeeping approach to control the overall type I (false positive) error rate. For each BOTOX dose versus placebo, each variable/dose pair will be examined for significance only if significance was determined for all variable/dose pairs ranked ahead of it.

A 2-sided test with a p-value ≤ 0.05 will be considered as statistically significant for the treatment group comparisons of each BOTOX dose (BOTOX 195 U and BOTOX 155 U) versus placebo.

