[for Europe]), and MSQ v2.1 RFR domain score at Month 6 will come from the same type of MMRM analysis of observed data used for the primary efficacy endpoint, except that the baseline covariates will be monthly headache days, monthly acute headache medication days, AIM-D Physical Impairment domain score (or HIT-6 score [for Europe]), and MSQ v2.1 RFR domain score, respectively.

Logistic regression will be used to analyze responder variables using the same ANCOVA analysis model described for the primary variable (i.e., the MMRM model used for the primary analysis, but without repeat measures). The proportion of subjects with at least 50% reduction in the change from baseline in monthly migraine days across Months 5 and 6 will be summarized, along with p-values from the logistic regression. The primary assessment will be the pairwise comparison of each BOTOX dose versus placebo.

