3. AIM-D PI responder across Months 5 and 6 using the cutoff of █: Individual-level score change of \leq █ points can be considered clinically meaningful; (i.e., a participant whose PI domain score of the AIM-D improves (decreases) by \geq █ points from baseline across Months 5 and 6 can be considered a responder).³ This MWPC threshold for the AIM-D PI was corroborated through psychometric evaluation and score interpretation analyses using the Phase 3 data (M21307/PRECLUDE).

For the MSQ v2.1 RFR and AIM-D PI responder endpoints defined above, a raw summary of the proportion of responders will be provided and comparisons of each BOTOX dose (195 U and 155 U) versus placebo will be done using logistic regression using the same ANCOVA analysis model described for the primary variable (i.e., the MMRM model used for the primary analysis, but without repeat measures). The analysis model will include treatment (BOTOX 195 U, BOTOX 155 U, and placebo), country and strata of █ as fixed effects, with the corresponding baseline as a covariate, included as a continuous variable. The analysis will be performed based on postbaseline values at the specific timepoints. The treatment difference in terms of odds ratio between each BOTOX dose group and placebo will be estimated and tested from these models.

9.6 [REDACTED]

At the end of the double-blind phase of study (Week 24), in order to evaluate treatment [REDACTED], the participant will be asked to indicate which [REDACTED] [REDACTED]. This assessment will include 2 questions: (1) The [REDACTED], and (2) [REDACTED]

[figure not shown]
The [REDACTED] assessment asks the participant to indicate the response using the scale below that best describes the [REDACTED] assigned:

For data summary, responses to the Question (1) above will be summarized on a 5-point scale: [REDACTED]

[REDACTED] The response frequencies will be summarized with descriptive statistics, but inferential statistics will not be generated. Interpretation of the results should be done with awareness that [REDACTED] is confounded with efficacy and safety.

The second question asks the participant to indicate the reason(s) why they chose their response to Question (1):

Response option selected on above question will be populated with the response option selected by the participant on Question (1).

The subject [REDACTED] will be calculated and presented for each treatment group.

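### The four continuous secondary MMRMs drop baseline monthly migraine days, a randomisation stratification factor, so these tests stay valid but can be slightly conservative and less precise

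*SAP*

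**What the plan says.** Protocol 5.8 and SAP 2.3 stratify randomisation by a redacted yes/no factor and by being at or above a redacted number of "monthly migraine days at baseline (yes/no"), within country.

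The fixed effects of the primary MMRM (SAP 9.3.3) are treatment, month, country, the redacted stratum and treatment-by-month. The model is fitted "with the baseline number of monthly migraine days as a covariate, included as a continuous variable rather than as the binomial stratification variable". Migraine days therefore enter that model once, in continuous form.

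For the continuous secondary endpoints, SAP 9.4.2 takes the same type of MMRM "except that the baseline covariates will be monthly headache days, monthly acute headache medication days, AIM-D Physical Impairment domain score"; HIT-6 (for Europe) and MSQ RFR are treated likewise, each baseline matched to its endpoint. Protocol 7.4 makes the same replacement: "except that the baseline covariates will be monthly headache days, MSQ v2.1 RFR domain score, monthly acute headache medication days". The two documents agree. The supplementary ANCOVAs for secondary endpoints in SAP 9.4.3 follow the same rule.

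The remaining secondary endpoint, 50% responder status, keeps baseline migraine days as its covariate (SAP 4.3.6, 9.4.2).

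**The concern.** Adjusting for an endpoint's own baseline is sound. The difficulty is that own baseline takes the slot of baseline migraine days instead of being added beside it. Country and the other stratum carry over from the primary model; only the migraine-day factor drops out, and no reason is given. Elsewhere the plan is explicit when it removes such a term: the subgroup analyses in SAP 9.7 say that the subgroup variable's own fixed effect is left out. The omission here may simply follow from reusing the covariate sentence.

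If a prognostic factor that randomisation has balanced is left out of the model, the reported standard error still contains its variance. Intervals are then wider than necessary and tests somewhat conservative. Four of five secondary endpoints are affected, which is 4 × 2 = 8 of the 5 × 2 = 10 secondary dose-by-endpoint hypotheses. Under SAP 13.0 one non-significant result ends all later claims, so even a small avoidable loss has some relevance.

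**Working it through.** **Inputs.** SAP 2.4: the calculations "assume a 2-sided false-positive error level of alpha = 0.05", and "259 subjects in each of the BOTOX dose groups and the placebo group at the primary time point will provide 90% power". The SD and the detectable differences are redacted, and no power is stated for any secondary endpoint. The partial correlation r of baseline migraine days with a secondary outcome, given own baseline and the other model terms, is not in the documents. It is an assumption here, varied from 0 to 0.3.

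**The plan's own figure.** The total is 3 × 259 = 777, as stated. The 259 cannot be reproduced independently because the SD and difference are redacted. Solving backwards, the standardised difference is (1.960 + 1.282) × √(2/259) = 0.285. This is circular and serves only as a reference point: a test with 90% power has an expected z of 1.960 + 1.282 = 3.24.

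**Standard error.** Leaving the covariate out multiplies the standard error by k = 1/√(1 − r²).

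**Power without the covariate, if it is 90% with it.** There are two limiting cases:
- Randomisation balances migraine days completely. The estimate is as precise as the adjusted one and only the reported standard error is too large: power = Φ(3.24 − 1.960 k).
- Randomisation does not balance migraine days at all. The estimate itself is noisier: power = Φ(3.24/k − 1.960).

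Stratifying on a yes/no cut of a count lies between the two.

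| r | k | Power, full balance | Power, no balance | Loss (points) |
|---|---|---|---|---|
| 0 | 1.000 | 90.0% | 90.0% | 0 |
| 0.1 | 1.005 | 89.8% | 89.7% | 0.2 to 0.3 |
| 0.2 | 1.021 | 89.3% | 88.8% | 0.7 to 1.2 |
| 0.3 | 1.048 | 88.2% | 87.1% | 1.8 to 2.9 |

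At r = 0.3, for example, Φ(3.24 − 1.960 × 1.048) = Φ(1.19) = 88.2%, and Φ(3.24/1.048 − 1.960) = Φ(1.13) = 87.1%.

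**In subjects.** In the no-balance case, recovering 90% needs 259/(1 − r²) per arm: 262, 270 and 285 at r = 0.1, 0.2 and 0.3, that is 3, 11 and 26 more per arm.

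**Type I error.** Under full balance at r = 0.3 the two-sided rejection rate is 2Φ(−1.960 × 1.048) = 4.0%. With no balance it is 5%. The omission cannot push it above the nominal level.

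**Simulation.** The check was a linear model at a single time point: 777 subjects, 1:1:1, randomised in blocks stratified at an assumed cut of 10 migraine days, 3,000 runs per setting, with the correlation between own baseline and migraine days set to 0.3 or 0.85. At r = 0.3 the mean standard error was 0.0879 without migraine days and 0.0839 with them, a ratio of 1.048 as the formula gives. Rejection under the null without the term ranged from 3.8% to 5.3% across settings (Monte Carlo error about 0.4 points). The lowest value came at r = 0.3 with the weak own-baseline correlation. Adding only the binary stratum recovered part of the gain (standard error 0.0850 or 0.0861). The simulation left out country, the other stratum and repeated measures.

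**The case against.** The strongest reply is that nothing here is wrong, only slightly less efficient than it could be. The covariate choice is prespecified and identical in both documents, and type I error is protected. The sample size rests on an unadjusted two-sample t-test and no power is promised for secondary endpoints, so no stated target is missed. Own baseline, country and the other stratum are already in the models. Eligibility confines migraine days to 6 to 14, which tends to weaken their predictive value. For headache days, own baseline is a close proxy because migraine days are a subset of headache days. All of this stands. It limits the size of the point but does not explain why the covariate should be removed.

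Several stronger readings are tempting, and the documents do not support them:

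- That every one of these tests does lose precision. This needs a non-zero partial correlation, which the documents do not give.
- That 88.2% is the worst case at r = 0.3. It assumes complete balance on continuous migraine days, whereas only a yes/no cut is balanced. It is the smallest loss at that correlation; the largest is the fall to 87.1%.
- That the whole 0.5% to 4.8% is variance that randomisation removed. Part of it is an ordinary covariate gain forgone.
- That the same argument covers the MSQ and AIM-D responder models in SAP 9.5.7, which are fitted "with the corresponding baseline as a covariate, included as a continuous variable" and also lack migraine days. Those are logistic models. Adding a prognostic covariate there typically raises the standard error of the log odds ratio and changes the conditional odds ratio, so the linear result does not carry over. They also lie outside the multiplicity control.

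The redacted stratum in the primary model is unlikely to be the migraine-day factor, because SAP 9.3.3 says that migraine days enter as a continuous covariate in place of that factor.

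**Conclusion.** The omission is established from the text: a stratification factor is absent, in either form, from the MMRMs for headache days, acute headache medication days, MSQ RFR and AIM-D Physical Impairment/HIT-6. The consequence is conditional and modest. Over the assumed range the cost in power stays below 3 points. Any material loss would fall mainly on the secondary endpoints other than headache days and responder status. The point concerns efficiency and consistency with the primary model, not validity. It merits a change because keeping the covariate costs almost nothing.

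**What to change.** In SAP 9.4.2 and Protocol 7.4, state that the endpoint's own baseline is added to the primary model and that continuous baseline monthly migraine days is kept as a covariate. If the sponsor prefers to leave it out, the SAP should say why.

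The change should be specified before randomisation codes are released. If that has already happened, the planned models should stand and the models with baseline migraine days should be reported as supplementary.

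The cost is one sentence in each document and one degree of freedom. SAP 4.1 and 9.2 state that every randomised subject has a baseline value for the primary variable, so no subject is lost. Correlation between the two baseline covariates does not harm the treatment contrast.

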5.6 Follow-Up After Subject Discontinuation of Study Drug or from Study

To minimize missing data for efficacy and safety assessments, subjects who prematurely discontinue study drug treatment should continue to be followed for all regularly scheduled visits, unless subjects have decided to discontinue study participation entirely (withdrawal of informed consent). Subjects should be advised on the continued scientific importance of their data even if they discontinue treatment with study drug early.

If a subject prematurely discontinues study participation (withdrawal of informed consent), the procedures outlined for the exit/PD visit (Week 48/Visit 14) should be completed as soon as possible, preferably within 2 weeks. In addition, if subject is willing, a 30-day follow-up phone call after the last dose of study drug may be completed to ensure all treatment-emergent AEs (TEAEs)/SAEs have been resolved.

In the event a subject withdraws consent from the clinical study, biomarker research will continue unless the subject explicitly requests analysis to be stopped. When AbbVie is informed the patient has withdrawn and no longer wishes biomarker samples research to continue, samples will not be analyzed, and no new biomarker analysis data will be collected for the withdrawn subject or added to the existing

data or database(s). Data generated from biomarker research, before subject withdrawal of consent, will remain part of the study results.

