For primary and secondary efficacy variables, in order to have data for all subjects in the ITT population for the ITT analysis, missing diary values (due to having reported less than 14 days of headache data in a 28-day period) will be estimated according to the primary imputation methods discussed in Section 9.3.2.7.

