9.3.2.7 Imputation Rule

In this study, the imputation methods are only intended for the diary data collected in the e-diary and secondary variables (i.e., MSQ v2.1 RFR domain score, AIM-D Physical Impairment domain score, HIT-6 score). No imputation will occur for other variables.

If a subject reports any diary data for less than 14 days of a 28-day period, the subject's scores (such as headache day count) for that period will be set to missing for summary tables of observed data. For tables of imputed data, such a subject's score for that period will be imputed by a modified last observation carried forward (mLOCF) rate-change method and rounded to the nearest whole number. Specifically, the substitution will be the subject's previous 28-day period score multiplied by the ratio of the mean within the same treatment regimen in the 28-day period of interest to the mean within the same treatment regimen in the previous 28-day period.

If a subject reports diary data for at least 14 days of a 28-day period, the scores for the period will be determined by the simple prorating method (discussed in Section [9.3.2.5](#)).

If a subject reports any diary data for less than 4 days of a 7-day period, the subject's scores (such as headache day count) for that period will be set to missing for summary tables of observed data. For tables of imputed data, such a subject's score for that period will be imputed by a modified last observation carried forward (mLOCF) rate-change method and rounded to the nearest whole number. Specifically, the substitution will be the subject's previous 7-day period score multiplied by the ratio of the mean within the same treatment regimen in the 7-day period of interest to the mean within the same treatment regimen in the previous 7-day period.

If a subject reports diary data for at least 4 days of a 7-day period, the scores for the period will be determined by the simple prorating method (discussed in Section [9.3.2.5](#)).

For example, for imputation of the 28-day period, the substitution will be iterative by 28-day period, in that imputation of a given 28-day period (e.g., Week 8) will follow

imputation of the preceding 28-day period (e.g., Week 4). The following is an example of how the mLOCF algorithm works:

Observed data:

Subject #	Treatment	Headache Day Count				
		Baseline	Week 4	Week 8	Week 12	Week 16
100001	TRT-A	14	12	13	---	---
100002	TRT-A	10	9	9	8	6
100003	TRT-A	12	13	10	8	5
100004	TRT-A	6	6	5	6	4

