9.4.2 Main Analyses of Secondary Efficacy Endpoints

The attributes of the estimands corresponding to the secondary efficacy objectives are summarized in [Table 2](#).

Table 2. **Summary of the Estimand Attributes Corresponding to the Secondary Efficacy Objectives**

Attributes of the Estimand					
Estimand Label	Treatment	Endpoint	Population	Handling of Intercurrent Events	Statistical Summary
Secondary 1	Arm A: Placebo Arm B: BOTOX 155 U Arm C: BOTOX 195 U	Change from baseline in the frequency of monthly headache days across Months 5 and 6	ITT Population	IE1: Missing data due to study discontinuations, will not be imputed and will be handled as MAR with MMRM. IE2: Regardless of whether rescue medications are taken or not, collected data will be included in the analysis. IE3: Subjects who discontinue study treatment due to any reason will have their data collected after discontinuation of study treatment, and collected data will be included in the analysis.	The difference in the change from baseline in the frequency of monthly headache days across Months 5 and 6 between each BOTOX dose group and placebo

Attributes of the Estimand					
Estimand Label	Treatment	Endpoint	Population	Handling of Intercurrent Events	Statistical Summary
Secondary 2	Arm A: Placebo Arm B: BOTOX 155 U Arm C: BOTOX 195 U	Responder status of 50% reduction from baseline in the frequency of monthly migraine days across Months 5 and 6	ITT population	IE1: Missing data due to study discontinuations, will not be imputed and will be handled as MAR with MMRM. IE2: Regardless of whether rescue medications are taken or not, collected data will be included in the analysis. IE3: Subjects who discontinue study treatment due to any reason will have their data collected after discontinuation of study treatment, and collected data will be included in the analysis.	The odds ratio in participants responder status of 50% reduction from baseline in the frequency of monthly migraine days across Months 5 and 6 between each BOTOX dose group and placebo

Attributes of the Estimand					
Estimand Label	Treatment	Endpoint	Population	Handling of Intercurrent Events	Statistical Summary

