9.5 Additional Efficacy Endpoints and Analyses

The other endpoints are listed in Section 3.3. Analysis of these variables will be performed at the nominal significance level, without adjusting for multiplicity. Hence,

results will be considered descriptive and potentially supportive of the results for the primary and secondary endpoints.

The comparisons of interest for each of the other endpoints will be the pairwise comparisons of each BOTOX dose (195 U and 155 U) versus placebo, with no statistical comparison between the BOTOX doses.

In general, though, for continuous and ordinal variables (e.g., headache days, acute headache medication days, [REDACTED], scale scores), the change from baseline analysis will be done with the same type of MMRM or ANCOVA analyses described in Section 9.3.3 and Section 9.3.4 for the primary efficacy endpoint, except that the baseline covariate will be for the variable being analyzed. For [REDACTED] which is recorded as change scores, baseline for [REDACTED] score will be used as a surrogate baseline covariate, to adjust for variation in response that is due to baseline differences between treatment groups.

In general, for responder variables (e.g., responder status of 75% or 100% reduction from baseline in the frequency of monthly migraine days, responder status of at least 5-grade improvement in total HIT-6 score), analysis of the responder status will be done with the same methods described in Section 9.4.2 for the secondary variable of 50% responder status.

For monthly migraine days across weeks, the change from baseline analysis will be done with the same type of MMRM or ANCOVA analyses described in Section 9.3.3 and Section 9.3.4 for the primary efficacy endpoint, except that the model will use weeks instead of months. The counts for a given week will be prorated to 28-day counts before calculating the change from baseline.

The decile responder status of t% (i.e., t is from 0 to 100 by tens) reduction from baseline in the frequency of monthly migraine days across Months 5 and 6, defined as a subject with at least a t% reduction from baseline in the 2-month average of monthly migraine days over Months 5 and 6, will be assessed for each individual.

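### The missing-data rule for the 50% responder endpoint names an MMRM, but the analysis is a one-record logistic regression on subjects with an observed Months 5-6 status

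*SAP*

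**What the plan says.** The relevant statements are these.

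- **SAP 9.4.2, Table 2, Secondary 2, IE1:** "Missing data due to study discontinuations, will not be imputed and will be handled as MAR with MMRM". The continuous secondary endpoints carry the same text.
- **SAP 9.4.2, analysis text:** "Logistic regression will be used to analyze responder variables using the same ANCOVA analysis model described for the primary variable". It explains that this is the primary model with the repeated measures taken out. SAP 4.3.6 also assigns binary variables to logistic regression.
- **Protocol 7.4:** It specifies the same logistic model but leaves a door open: "GLIMMIX models for repeated measures of binary data might be used in place of MMRM models; if so, the methodology will be described". The SAP describes no such model.
- **Protocol 7.4, on imputation:** "A sensitivity analysis will use the same logistic model after imputation of missing data for the underlying primary variable by the mLOCF rate-change method".
- **SAP 9.3.2.7:** When a 28-day period has fewer than 14 reported diary days, the score "for that period will be set to missing for summary tables of observed data". The mLOCF value is used only in tables of imputed data.
- **SAP 9.3.2:** Missing diary values for primary and secondary variables "will be estimated according to the primary imputation methods discussed in Section 9.3.2.7".
- **SAP 9.5:** The decile responder is defined by "at least a t% reduction from baseline in the 2-month average of monthly migraine days over Months 5 and 6". SAP 4.3.7 rounds that average to a tenth.
- **SAP 9.3.4:** Monthly migraine days will be multiply imputed by treatment group, with 30 datasets, as a sensitivity analysis of the primary endpoint.

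**The concern.** An MMRM uses every observed month. A subject who leaves after Month 3 still contributes, and missingness may depend on the responses already seen. A logistic regression with one record per subject cannot do this. If nothing is imputed, a subject without a Months 5-6 status drops out of the model, and that subject's Months 1-4 counts are not used.

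The endpoint is under type I error control, and SAP 13.0 stops testing at the first failure, so later tests depend on it. SAP 9.5 and 9.5.7 apply the same logistic method to other responder variables. If withdrawal is related to earlier response and the relation or the rate differs between arms, the odds ratio is biased, in either direction. The responder percentages to be reported can be too high even when the odds ratio is nearly right.

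**Working it through.** **1. Which rule governs the main analysis?** IE1 rules out imputation and names an MMRM. The analysis text names a logistic model without repeated measures. The sentence in SAP 9.3.2, read alone, would mean mLOCF in the main analysis. But SAP 9.3.2.7 confines mLOCF to tables of imputed data, and both Protocol 7.4 and SAP 9.4.3 call the imputed logistic model a sensitivity analysis. The consistent reading is an observed-data logistic model. It is valid if missingness depends only on the model terms: treatment, country, stratum and baseline.

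**2. Figures in the plan.** 259 per arm (3 x 259 = 777) is set for the primary endpoint. Its difference, SD and effect size are redacted. No responder rate, dropout rate or power is given for this endpoint, so there is no stated figure to reproduce.

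**3. Assumed inputs.** Monthly counts were simulated for three arms of 259, with 1500 trials per scenario. Baseline was 6-14 days, the SD of change in the Months 5-6 average was 3.3, and correlations between months were 0.71-0.79. Full-data response was about 33% on placebo and 44% on BOTOX. The adjusted full-data odds ratio (OR) was 1.62, with power 74%. The dropout hazard after Months 1-4 depended on the last observed percent change, with odds x1.16 (moderate) or x1.35 (strong) per 10 points less reduction. Resulting true response among dropouts, placebo/BOTOX, was about 20%/29% (moderate) and 11-12%/16-19% (strong).

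**4. Hand check.** With true rate p, dropout fraction m and response q among dropouts, the rate in those who remain is

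p_obs = (p - m q) / (1 - m).

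Take p = 0.328 and 0.440 from a large unadjusted run. The full-data OR is (0.440/0.560)/(0.328/0.672) = 1.61. For strong dependence use mid-values q = 0.115 and 0.175.

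Worked case, one common strong mechanism, with dropout of 11.0% on placebo and 9.0% on BOTOX:
- placebo: (0.328 - 0.110 x 0.115)/0.890 = 0.354
- BOTOX: (0.440 - 0.090 x 0.175)/0.910 = 0.466
- OR = (0.466/0.534)/(0.354/0.646) = 1.59

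| Dropout, placebo / BOTOX | Dependence | OR by formula (full 1.61) | OR simulated (full 1.62) |
|---|---|---|---|
| 10% / 10% | none | 1.61 | 1.62 |
| 10% / 10% | moderate; strong | 1.62; 1.63 | 1.63; 1.64 |
| one mechanism: 10.6% / 9.4%; 11.0% / 9.0% | moderate; strong | 1.60; 1.59 | 1.61; 1.59 |
| 12.5% / 8% | moderate; strong | 1.56; 1.54 | 1.57; 1.55 |
| 8% / 12.5% | moderate; strong | 1.67; 1.73 | 1.67; 1.71 |
| about 10%, placebo only dependent | strong | 1.45 | 1.46 |
| about 10%, BOTOX only dependent | strong | 1.81 | 1.83 |

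Two simulation runs of the 8% / 12.5% strong case gave 1.71 and 1.74, so read that cell as about 1.7.

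**5. Which rows share a mechanism?** A truly common mechanism separates the arms only to 10.6%/9.4% or 11.0%/9.0%. To reach 12.5%/8%, dropout odds on placebo must be 1.44 (moderate) or 1.33 (strong) times those on BOTOX at the same observed response.

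**6. Proportions.** With 10% dropout in each arm, the formula gives 34.2%/45.7% (moderate) and 35.2%/46.9% (strong), against 32.8%/44.0%. That is a rise of 1.4 to 2.9 points with the OR almost unchanged.

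**7. Power and multiple imputation.** Random dropout of about 10% lowers power from 74% to 70%; multiple imputation gives 73%. Imputation returned 1.615-1.624 wherever missingness was random or depended on observed data. When dropout depended on the unseen next month it was not unbiased: 1.60 at 12.5%/8%, and 1.58 or 1.66 in the one-arm cases.

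**8. One evaluable month.** No section says how to classify such a subject. If 5% of remaining subjects are affected (about 12 per arm), about 11% of them, 1-2 per arm, change class, and the OR stays at 1.55 in the strong 12.5%/8% case.

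**The case against.** The best defence is that little is hidden and little is at stake. IE1 does say that missing data are not imputed. A logistic model on observed outcomes is itself valid under missing at random given its covariates, so only the reference to the MMRM is plainly wrong. Exposure is limited by design: "subjects who prematurely discontinue study drug treatment should continue to be followed for all regularly scheduled visits", IE3 keeps their data in the analysis, and a month counts with half its diary days. An mLOCF version of the responder analysis is specified in Protocol 7.4, and the SAP version history records its addition. Multiple imputation also reverses the no-imputation clause and alters a protocol-specified main analysis.

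Most of this stands. A reader might infer that missing at random is simply false here; it is narrower than the text implies, not false. A reader might also infer that everyone who stops study drug is dropped; the follow-up rule and IE3 say otherwise. What does not stand is that the plan is workable as written. IE1 names a method that this endpoint does not use, and nowhere states the assumption that replaces it. IE1 also covers only study discontinuation, not months with too few diary days.

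**Conclusion.** The contradiction is certain from the text; material bias is not shown. It should be fixed because a type-I-controlled endpoint has a missing-data rule that cannot be carried out, and because the analysis actually specified rests on a narrower, unstated assumption.

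On assumed inputs, random dropout, or equal rates under the same mechanism, leaves the odds ratio essentially unbiased with some loss of power. One common response-dependent mechanism at about 10% average dropout lowers it from about 1.62 to 1.59-1.61. The range of about 1.55 to 1.71 needs dropout odds that differ between arms at the same observed response. Values of 1.46 or 1.83 need response-dependent dropout in one arm only. Observed proportions rise by about 1 to 3 points in either case.

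A reader might infer that the responder test is seriously biased or that type I error is inflated. The documents support neither. They give no dropout rate and nothing to suggest arm-specific mechanisms. If treatment had no effect on the monthly counts and dropout followed one mechanism, the arms would be exchangeable and the complete-case odds ratio would centre on 1.

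**What to change.** **Preferred.** Derive responder status from the imputed Months 5-6 average in the 30 datasets already planned in SAP 9.3.4, fit the same logistic model to each and pool by Rubin's rules. Name baseline and all months as imputation predictors, since SAP 9.3.4 names none. Replace the IE1 text for Secondary 2, including the no-imputation clause, with this method, and list the change in SAP 14.1. This also settles the one-month case. A repeated-measures binary model, which Protocol 7.4 allows, is an alternative, but it models monthly response rather than response on the two-month average.

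**If the observed-data logistic model is kept.** Remove the reference to the MMRM from IE1, state that missingness is assumed to depend only on the model covariates, give a rule for one evaluable month, and make the imputed version a firm sensitivity analysis.

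**Minor wording, in either case.** Align the SAP 9.3.2 sentence with the rule chosen. Reword SAP 9.4.3, which says that secondary sensitivity analyses are not planned and then describes one, so that the mLOCF responder analysis is clearly planned.

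**Cost.** SAP text, one entry in 14.1 and modest programming on existing imputations; no new data. The price is reliance on the imputation model, with no protection if dropout depends on unseen outcomes.
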